7.5.4. Management of Potential Myocardial Toxicity and ECHO / MUGA Changes

SQ3370 should be stopped at the first sign of impaired cardiac function. ECG changes such as dysrhythmias or conduction delays may be indicative of anthracycline-induced cardiomyopathy. A 10% decline in LVEF to below the lower limit of normal or an absolute LVEF of 45% or a 20% decline in LVEF at any level is indicative of deterioration in cardiac function. In general, if test results indicate deterioration in cardiac function associated with SQ3370, the benefit of continued treatment should be carefully evaluated against the risk of producing irreversible cardiac damage. Acute life-threatening arrhythmias have been reported to occur during or within a few hours after conventional Dox administration.

Other events such as myocardial infarction, anginal symptoms, elevated serum troponin-T, or symptoms or signs of new congestive heart failure should be reported to the Sponsor immediately and Investigational Product administration should be halted. The patient should be evaluated and if there appears to be significant evidence of myocardial injury, study treatment should be discontinued permanently.

7.5.5. Management of Myelosuppression

Myelosuppression is a well-known toxicity of Dox and may be dose-limiting for SQ3370. Standard oncologic management of cytopenias, including neutropenia, febrile neutropenia and sepsis or bleeding due to thrombocytopenia should be instituted if indicated.

7.5.6. Management of Hepatotoxic Risk

Investigators should monitor the patient for elevated levels of AST and/or ALT concurrent with abnormal elevations in total bilirubin that meet the criteria outlined below in the absence of other causes of liver injury and investigational treatment should be stopped as they are considered potential cases of drug-induced liver injury (DILI).

The following laboratory values should be evaluated for Hy's Law cases taking into consideration specific clinical symptoms of the patient and evaluation of other causes of hepatic impairment:

- Aminotransferases (AT), ALT or AST elevation > 3 times the upper limit of normal (ULN); AND
- Total bilirubin (TBL) > 2 times ULN, without initial findings of cholestasis (elevated serum alkaline phosphatase); AND

- No other immediately apparent possible causes of AT elevation and hyperbilirubinemia, including but not limited to viral hepatitis, pre-existing chronic or acute liver disease, or the administration of other drug(s) known to be hepatotoxic.

Patients with labs that are suspicious of DILI should return to the clinic as soon as possible, or at least within 48 hours, to be evaluated with laboratory tests, a detailed history and physical assessment.

The possibility of other causes for elevated liver function tests should be evaluated. Further testing for acute hepatitis A, B, or C infection and liver imaging (e.g., biliary tract) at a minimum may be warranted.

If on the repeat laboratory testing for drug induce liver injury (DILI), results continue to meet the threshold listed above, and after a thorough evaluation for alternative explanations fail to provide a clear clinical explanation, the ongoing hepatic injury, per protocol, the diagnosis should be DILI. ALL investigational treatment should be stopped as they are considered potential cases of drug-induced liver injury.

7.6. DOSE MODIFICATIONS

7.6.1. Missed Doses

SQL70 Biopolymer Missed Doses: The injection of SQL70 biopolymer cannot be missed; it must be injected prior to SQP33 protodrug infusion. If the SQL70 biopolymer injection is missed on Day 1 of any cycle, alert the Medical Monitor immediately and do not inject SQP33 protodrug.

SQP33 Protodrug Missed Doses: Missed infusions of SQP33 protodrug may be made up, but only on Day 6. The Medical Monitor should be alerted immediately in the case of any missed infusions.

Example: SQP33 protodrug infusions occur as scheduled on Day 1 and Day 2, but, due to extenuating circumstances (snowstorm, family emergency, etc.), the patient cannot attend their Day 3 visit. The Day 3 SQP33 protodrug infusion and other study procedures are therefore skipped and dosing resumes on Day 4 and Day 5. The missed dose may be made up on Day 6. If the dose cannot be made up on Day 6, then the patient only receives 4 infusions (Day 1, 2, 4, and 5) during that cycle.

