Dox was detected at the local site. In rats, SQL70 biopolymer rapidly captured and rendered SQP33 protodrug undetectable in plasma samples within 30 minutes of administration, with measurable conversion to active Dox. SQP33 protodrug was stable in vivo, showing minimal nonspecific conversion to active Dox in the absence of SQL70 biopolymer, based on plasma exposure levels. Plasma exposure to active Dox was highest when SQP33 protodrug was given between 1 to 24 hours after SQL70 biopolymer injection. Liver exposure to active Dox peaked when SQP33 protodrug was given 24 hours after SQL70 biopolymer injection. Plasma and liver exposure to active Dox decreased drastically when SQP33 protodrug was given 96 hours (Day 5) after SQL70 biopolymer injection. Active Dox concentrations at the SQL70 biopolymer site suggest local conversion of systemic SQP33 protodrug to active Dox even 5 days after SQL70 biopolymer injection.

A Good Laboratory Practice (GLP)-compliant study in dogs showed that a single 10 mL local injection of SQL70 biopolymer could continue to capture 26.5% of the SQP33 protodrug given systemically on the fifth day of a 5-day regimen. In a separate GLP bridging study in dogs, plasma samples (collected up to 3 days after the animals received a single local SQL70 biopolymer injection) and liver samples (collected on Day 6) reacted with a TCO-containing internal standard (IS), suggesting the presence of SQL70 biopolymer in the plasma and the liver. Plasma samples collected on Day 4 and 5 did not react with the IS.

In summary, the studies suggest that a fraction of the locally injected SQL70 biopolymer circulates in the plasma from Day 1 to Day 3, leading to active Dox exposure that peaks in the plasma between Day 1 and 2, and peaks in the liver around Day 2. Active Dox exposure in the plasma and liver decrease markedly by Day 4 and 5. SQL70 biopolymer at the local site continues to transform systemic SQP33 protodrug into active Dox at least until Day 5 following local SQL70 biopolymer injection.

Toxicology

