3.1.4. Treatment

3.1.4.1. Treatment Cycles

An individual cycle of treatment is defined as a 3-week (21-day) period wherein the SQL70 biopolymer is injected into a lesion or lesions on Day 1 followed by 3-5 consecutive daily infusions of SQP33 protodrug (Day 1-5 or in Phase 2a Group 2 subset will receive Day 1-3). In Phase 1 subjects assigned to receive 20 mL SQL70, no more than 2 lesions may be injected (10 mL each) during the treatment cycle with the exception of a “regional cluster of lesions”

defined as tumors that are contiguous, in apposition to each other, or are within 5 cm of each other. If there is a question whether a lesion or lesions are appropriate for injection, the Medical Monitor should be consulted.

Phase 2a Groups Specific Treatment Cycles

All patients treated at the RP2D in all groups within the Phase 2a will not be treated beyond 12 cycles or approximately 8 months.

The table below provides an overview of the SQL70 volume administered per lesion, number of potential lesions to inject, number of SQP33 timepoints per cycle and the dose to be administered each day.

Table 1: Expansion Group SQ3370 Administration Overview

Group	SQL70 Biopolymer (mL/Route)	SQP33 Protodrug RP2D IV	Daily % Dose
1: Extremity STS	20 mL intratumorally	x 5 days	20% daily x 5
2: Unresectable STS (SQP33 comparison 3 day vs 5 day)	10 mL intratumorally	x 5 days	20% daily x 5
		x 3 days	20% day 1 only 40% day 2 and 3 No Dosing on Day 4 or 5
3a: Head and Neck	10 mL intratumorally	x 5 days	20% daily x 5

Group 1: Advanced High-risk Soft Tissue Sarcoma of the Extremity

Patients will enroll at the RP2D of SQP33 given over 5 days and will receive a fixed dose of SQL70 (20 mL). On Day 1 of each cycle, the subject will receive an injection of the SQL70 biopolymer into the tumor, followed by five (5) days of SQP33 infusion at the RP2D within 3 hours \pm 30 minutes. All patients are planned to receive 2 cycles of SQ3370 and undergo a disease reevaluation per RECIST 1.1. All patients without evidence of disease progression (PD) after 2 cycles, will then undergo an additional 2 cycles of treatment and have a presurgical disease re-evaluation and proceed to definitive surgical procedure(s).

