Only patients who have had objective evidence of response, or whom in the opinion of the multidisciplinary treatment team, have achieved a clinical benefit may defer surgery at this point, and the study will allow up to 4 additional pre-op cycles, at which point patients should undergo exploratory surgery and or tumor resection. It is recommended that the surgical team place markers at the tumor margins to direct SQL70 dosing post resection. Post operatively subject with good responses may receive up to 4 additional cycles but not to exceed 12 cycles within the study. Surgical markers will be used to indicate the tumor bed for injection with SQL70.

Any patient at any point who has been determined to have progressive disease has reached the end of treatment and will proceed to a definitive surgical treatment. Note: pre-operative radiation

is allowed for patients with PD pre-operatively on study at this point. It is encouraged to keep subjects on study and to evaluate surgical specimens as per planned biomarker and pathological assessments. See [Schedules of Assessments Appendix H](#).

Group 2: Unresectable Soft Tissue Sarcoma with a Comparison of the RP2D of SQP33 administered over 3 vs 5 days

Patients will enroll at the RP2D of SQP33 given over 3 or 5 days and will receive a fixed dose of SQL70 (10 mL) on Day 1 of each cycle.

To compare safety and tolerability of the RP2D in two infusion schedules of SQP33 (3-day vs 5-day) in locally advanced, unresectable, each treatment group will maintain the total dose of SQP33 per cycle and compare two different infusion schedules while receiving the same dose and timing of SQL70. All subjects will commence treatment with SQP33 within 3 hours ± 30 minutes.

Table 2: Group 2 SQP33 Protodrug RP2D (% Administered) Per Day

	Day 1	Day 2	Day 3	Day 4	Day 5
5-Day Administration	20%	20%	20%	20%	20%
3-Day Administration	20%	40%	40%	NO Treatment	NO Treatment

See Pharmacy Manual for additional details.

Any patient at any point who has been determined to have progressive disease has reached the end of treatment, any subject completing 12 cycles of treatment will also have been deemed to have reached the end of treatment. See [Schedules of Assessments Appendix I](#) and [Appendix J](#).

Group 3a: Head and Neck

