5.3.2. SQP33 Protodrug Dosage and Administration

For reference, summary information is provided below. Details for study team members handling or administering IP are listed in the protocol-specific Pharmacy Manual.

SQP33 protodrug is administered once per day on Day 1 through 5 of each cycle (Expansion Group 2: Unresectable STS will also have a group receiving SQP33 protodrug once per day on Day 1 through 3 of each cycle). On Day 1, SQP33 protodrug infusion should start 3 hours (\pm 30 min) after SQL70 biopolymer injection. On Day 2 through 5, SQP33 protodrug infusion should start each day within \pm 2 hours of the Day 1 infusion start time for that cycle.

SQP33 protodrug vials should be removed from refrigeration and kept protected from light for 60 minutes to warm up to room temperature passively (22 °C to 28 °C, not to exceed 28 °C). The vial should NOT be warmed by placing in a microwave or in a hot water bath.

Once at room temperature, SQP33 protodrug is reconstituted with sterile water within each product vial. During reconstitution, the vial should be gently swirled to ensure full dissolution. The vial should NOT be vigorously shaken or inverted.

The reconstituted SQP33 protodrug solution is then added to saline IV bags at the appropriate concentration for IV infusion for the given dose level. One or more vials of SQP33 protodrug may be needed depending on the dose level.

Precautions: See section [7.5.2 Management of SQP33 Protodrug Infusion Reactions](#) regarding infusion reactions.

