APPENDIX J – SCHEDULE OF ASSESSMENTS – EXPANSION GROUP 2: UNRESECTABLE STS (3 DAY)

Study Day	Screening	Treatment				SFTY FU	LTFU
		Week 1			Week 2		
		Day 1 ^a	Day 2	Day 3	Day 10 ± 2 days		
On-Site	On-Site	On-Site	On-Site	On-Site	Telephone or On-Site ^b	On-site	Variable ^m
Screening	Informed consent ^c	X					
	Medical history	X					
	Review Inc/Exc Criteria	X					
	Confirm Eligibility		X				
Safety	Physical Exam	X					
	Symptom-Directed PE		X ^d			X	
	Vital Signs	X	X	X	X	X	
	ECHO or MUGA	X	Every other cycle ^e			X ^k	
	Triplecate 12-Lead ECG	X	X ^{d, f}	Cycle 1 Only	Cycle 1 Only	X	
	ECOG	X	Cycle 2+			X	
	AE Review		X	X	X	X	
Labs	Conmed Review	X	X	X	X	X	
	Hematology & Chemistry	X	X ^d	Cycle 1 Only	X	Cycle 1 Only ^d	X ^d
	Coagulation & Urinalysis	X					X ^d
	Pregnancy Test	X ^g	X ^d				X ^d
	Serology	X					
	Plasma PK		See Separate PK Schedule				
	PBMC / ctDNA		Cycle 1, 2, 3 ^o				
IP	Cardio Tox Biomarkers	X	Every other cycle ^e			X	
	Tumor Biopsy		Cycle 1, 2, 3 only ^h				
Survival	CT / MRI & RECIST	X	Every 6 weeks ⁱ			X ^l	X ⁿ
	Administer SQL70 Biopolymer		X				
	Administer SQP33 Protodrug		X ^j	X	X		
Vital Status							X

Notes For APPENDIX J – Schedule of Assessments –EXPANSION GROUP 2: UNRESECTABLE (3 DAY)

- A - Day 1-3 can begin on any day that allows for the completion of the three consecutive treatments within the week.
- B - Day 10 visit may be performed via telephone (using a lab closer to a patient's home) or on-site.
- C - Written informed consent must be obtained prior to any study-specific procedures.
- D - May be performed up to 3 days before the visit.
- E - ECHO/MUGA to be performed every other cycle starting at Cycle 3; may be performed up to 7 days before the visit. Serum sample for cardiotoxicity biomarker analysis is to be collected on the same day.
- F - ECG to be performed pre dose and post dose +30 minutes.
- G - To be collected \leq 7 days prior to Cycle 1 Day 1 for women of child-bearing potential.
- H - Collect optional biopsy unless the tumor is considered too small to be biopsied; biopsy can be performed during screening and up to 4 days prior to Day 1 for other cycles.
- I - May be performed up to 7 days prior to the projected every 6 weeks from C1D1 date.
- J - SQP33 protodrug infusion occurs within 3 hrs \pm 30 mins after receiving SQL70 biopolymer injection.
- K - ECHO or MUGA not required at the Safety Follow-Up visit if performed in the previous 14 days.

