13. PHARMACOKINETIC (PK) ANALYSIS

PK in tumor and plasma and binary variable exploratory analyses will be performed by the Shasqi R&D group and/or sponsor PK consultant and is not part of this SAP. A separate PK data analysis plan will be developed prior to the database lock.

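### The Day 6 make-up rule for missed SQP33 infusions fits the 5-day schedule but not Group 2's 3-day arm, where a missed Day 2 or 3 infusion is either lost or given three days after the regimen ends

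*Protocol*

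**What the plan says.** Protocol section 7.6.1 (Missed Doses) says "Missed infusions of SQP33 protodrug may be made up, but only on Day 6", and asks that the Medical Monitor be alerted at once to any missed infusion. The rule names no group or schedule. Its only worked example is a 5-day patient who misses Day 3 and, if Day 6 is not possible, ends the cycle with four infusions.

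Section 5.3.2 describes a second schedule: "Expansion Group 2: Unresectable STS will also have a group receiving SQP33 protodrug once per day on Day 1 through 3 of each cycle". Table 1 in section 3.1.4.1 gives its daily shares as "20% day 1 only 40% day 2 and 3 No Dosing on Day 4 or 5", and Table 2 repeats them. The same section says that, to compare the two infusion schedules, "each treatment group will maintain the total dose of SQP33 per cycle". Appendix J, note A, adds that "Day 1-3 can begin on any day that allows for the completion of the three consecutive treatments within the week".

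Neither the protocol nor the Phase 2a SAP gives a separate missed-dose rule for the 3-day arm. The protocol refers to a Pharmacy Manual for further dosing detail; that manual is not among the documents.

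**The concern.** The rule appears to have been written for five daily infusions and carried over when the 3-day arm was added. In the 5-day schedule a Day 6 make-up extends the run of infusions by one day. In the 3-day arm the two days nearest to the planned run are closed twice: by section 7.6.1, which allows only Day 6, and by Tables 1 and 2, which bar dosing on Days 4 and 5. A site that follows the protocol exactly must therefore drop a 40% infusion or give it after a gap that the 3-day schedule was never meant to contain.

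Group 2 compares the safety, tolerability and PK of two schedules at the same total dose per cycle. A cycle at 60% of planned dose is not an equal-dose cycle, and a cycle dosed on Days 1, 2 and 6 is not a 3-day cycle. Both would still be summarized as 3-day treatment.

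**Working it through.** **Inputs.** Daily shares from Tables 1 and 2: 5-day arm 20% on each of Days 1 to 5; 3-day arm 20%, 40%, 40% on Days 1 to 3. Make-up day from section 7.6.1: Day 6.

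**The plan's own figures.** 5-day: 5 × 20% = 100%. 3-day: 20% + 40% + 40% = 100%. The equal total dose reproduces. The example in section 7.6.1 (four of five infusions) gives 4 × 20% = 80%.

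**One missed infusion.** Dose left if omitted = 100% − share of the missed day. Gap to make-up = 6 − last planned infusion day.

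| Schedule | Missed day | Dose left if omitted | Day 6 minus last planned day |
|---|---|---|---|
| 5-day | any | 100 − 20 = 80% | 6 − 5 = 1 day |
| 3-day | Day 1 | 100 − 20 = 80% | 6 − 3 = 3 days |
| 3-day | Day 2 or 3 | 100 − 40 = 60% | 6 − 3 = 3 days |

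If Day 3 is the missed day in the 3-day arm, the last infusion actually given is on Day 2, so a Day 6 make-up follows it by 6 − 2 = 4 days. A Day 4 make-up would follow it by 4 − 2 = 2 days.

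**Mean dose lost.** Let each infusion be missed with probability m, with no make-up. 3-day: m × (20 + 40 + 40) = 100m percent of the cycle dose. 5-day: 5 × m × 20 = 100m percent. The two are equal for every m. The documents give no value of m. For an assumed 2% to 5%, both arms lose 2% to 5% on average. Cycles with at least one miss are more common in the 5-day arm: 1 − (1 − m)^5 = 9.6% to 22.6%, against 1 − (1 − m)^3 = 5.9% to 14.3%.

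**Calendar, for a Monday-to-Friday clinic.** Monday start: Day 4 is Thursday, Day 5 Friday, Day 6 Saturday. Tuesday start: Day 4 is Friday, Day 6 Sunday. Wednesday start, which note A of Appendix J permits: Days 4 and 5 are Saturday and Sunday, Day 6 is Monday. So Day 4 is the easier day for the first two starts and Day 6 for the third.

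**The case against.** The strongest reply is that the rule is permissive and supervised. It restores the full dose whenever Day 6 is used, the Medical Monitor hears of every miss, section 5.7 monitors dosages and visit intervals, SAP section 8.5 reports the two schedules in separate columns, and SAP section 10.8 tabulates cumulative dose. The Pharmacy Manual may also hold guidance. This stands as a reason to rate the point low. It does not remove the point: alerting the Medical Monitor authorizes no other day, and nothing in the protocol or SAP reopens Day 4 or 5.

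A second reply is that dosing on Day 4 or 5 also breaks the three-consecutive-day schedule, and that removing Day 6 altogether would cost an infusion after a Wednesday start. The first part is true, but the departure is smaller than with Day 6. The second part is met by keeping Day 6 as a last resort.

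Three stronger readings are tempting, and the documents do not support them:

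- A reader might infer that the 3-day arm will be systematically under-dosed. At equal miss rates the mean loss is identical; only the size of a single shortfall differs (40% against 20%).
- A reader might want to count the patients left at 60% of dose. Such a count needs a miss rate that the documents do not give. It would also have to assume that nobody uses the permitted Day 6 make-up, so it would measure missed infusions and not the effect of the rule.
- A reader might infer that a Day 6 infusion would not be activated. Section 1.2.1 says that biopolymer at the local site "continues to transform systemic SQP33 protodrug into active Dox at least until Day 5". That is a lower bound. It does not show that activation is absent on Day 6, and any such doubt would apply equally to the 5-day arm.

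**Conclusion.** The point holds as a minor correction to a dosing rule. Read as written, section 7.6.1 leaves a 3-day patient who misses Day 2 or Day 3 with either 60% of the cycle dose or a 40% infusion three days after the planned end. The corresponding figures for a single miss in the 5-day arm are 80% and one day. These follow directly from Tables 1 and 2 and need no assumption about how often infusions are missed.

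How many cycles would be affected cannot be stated from the documents. The comparison is non-randomized, with 11 patients per arm and no power claim, so the consequence is some blurring of the schedule contrast in the affected cycles. No sample size, alpha or power changes. The conclusion assumes that the Pharmacy Manual contains no separate rule for the 3-day arm.

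**What to change.** In section 7.6.1, keep Day 6 as the make-up day for the 5-day schedule. For the 3-day arm, allow a missed infusion to be made up on the earliest feasible day from Day 4: Day 4, otherwise Day 5, with Day 6 as a last resort after Medical Monitor agreement. Add a footnote to Tables 1 and 2 saying that a make-up is the only exception to the bar on dosing on Days 4 and 5.

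The cost is one protocol sentence and one table footnote, with no extra patients. The small downside is that exception to a table entry that is now absolute. Because Day 6 remains available, a Wednesday start loses nothing.

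Two reporting additions are optional. SAP section 10.8 could show, by Group 2 arm, the percentage of planned cycle dose delivered and the number of cycles completed on the assigned days. The PK plan could flag cycles with a missed or made-up infusion; it is still to be written (SAP section 13: "A separate PK data analysis plan will be developed prior to the database lock"). All treated patients and cycles should stay in the main safety summaries.

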7.6.2. Dose Reductions

SQL70 Biopolymer Volume: The volumes of SQL70 biopolymer under study are 10 mL or 20 mL. Please consult the medical monitor if there are questions regarding the volume of SQL70 to be injected.

- **Dose reductions:**
 - **Phase 1:** The SQL70 biopolymer volume in the 20 mL group may be reduced from 20 mL to 10 mL if 20 mL is not tolerated. If a dose reduction occurred and two lesions are being treated the investigator will need to choose a single lesion to inject with 10 mL of SQL70 biopolymer.

- **Phase 2a:** The SQL70 biopolymer volume in the 20 mL group may be reduced from 20 mL to 10 mL if 20 mL is not tolerated.

SQP33 Prodrug Dose:

- **Dose reductions:**
 - **Phase 1 and Phase 2a:** If a patient does not tolerate their initial or subsequent dose level of SQP33 prodrug the patient may be treated with a 25% reduction in SQP33 prodrug dose.

7.6.3. SQ3370 Treatment Interruptions

The Medical Monitor should be notified if the Investigator intends to interrupt SQ3370 treatment either during or in between cycles for any reason.

